2.2. Background

CCL17, previously known as thymus and activation regulated chemokine (TARC), is a member of the CC-family of chemokines that binds and signals through the G-protein coupled CC-chemokine receptor, CCR4 [Imai, 1996; Imai, 1997]. CCL17 is produced by numerous immune and non-immune cell types. CCR4 is predominantly expressed on Th2 cells but is also present on other immune and non-immune cell types.

GSK3858279 is a high affinity ($K_d < 1\text{pM}$), human immunoglobulin G2 σ (IgG2 σ) (Fc-silenced), first-in-class, monoclonal antibody (mAb), binding specifically to the chemokine CCL17. It functionally inhibits CCL17 activating the chemokine receptor CCR4, to prevent downstream consequences of CCR4 signalling.

At the time of this protocol, GSK3858279 is being developed for treatment of osteoarthritis pain, however non-clinical data suggests an opportunity to treat other chronic pain conditions including neuropathic pain by targeting this pathway. Alleviating chronic pain is a major unmet need as current therapies (e.g. NSAIDs, opioids) have significant side effects and addiction liabilities that prevent their effective use in treating the patient's pain.

Rationale for CCL17 neutralisation in OA pain has been generated in vivo pre-clinically in inflammatory and arthritis models. CCL17 has been recently identified as a peripheral mediator of inflammatory pain and can itself induce arthritis. Intraplantar injection of recombinant CCL17 resulted in pain in mice in a CCR4-dependent manner [see IB, GlaxoSmithKline Document Number [RPS-CLIN-004032](#)

whilst therapeutic dosing with anti-CCL17 surrogate mAb inhibited established inflammatory pain [in house data - see IB, GlaxoSmithKline Document Number [RPS-CLIN-004032](#)]

Absence of CCL17 ameliorated inflammatory pain in various murine arthritis models.

In parallel, in a preclinical *in vivo* model of nerve injury that recapitulates the mechanical hypersensitivity and thermal allodynia presented by neuropathic pain patients, therapeutic dosing of anti-CCL17 surrogate mAb reverses pain [see IB, GlaxoSmithKline Document Number [RPS-CLIN-004032](#)]

Importantly, in contrast to inflammatory and arthritic models, chronic neuropathic pain and the rodent nerve injury models tested are largely insensitive to NSAID treatment. As such, the mechanism of action of analgesia induced by neutralisation of CCL17 is potentially applicable to neuropathic pain conditions considered refractory to NSAIDs. The opportunities to treat pain by targeting CCL17 in the context of a variety of conditions and aetiology needs to be explored clinically.

The PainCart is an integrated, multi-modal pain task battery of tests designed to investigate the efficacy of analgesic compounds against several types of pain, including thermal, electrical, chemical and mechanical pain. The models applied in the PainCart have been tested for predictive validity and reliability and can be used repeatedly, quickly, in short succession in healthy participant studies and patient studies.

The translation of findings from animals, through human pain models to patients (and back) is one of the greatest challenges in modern (pain) research. One major disadvantage of many human pain models is that they do not represent the pain aetiology or pain entity when they are translated to patients, i.e. they may mimic aspects of the clinical pain condition, but they cannot reflect the full multidimensionality of a disease. In addition, the main limitation of models of pain is the inability to replicate spontaneous pain, which is one of the main complaints of chronic pain patients and there are currently no human models available to measure this. This being said, experimental pain models may be used to mimic certain aspects of chronic pain condition such as sensitization of the peripheral or central pain processing (windup of nociceptors via repetitive electrical stimulation), or by inducing inflammatory pain responses, additional measures of central sensitization may be taken which portray aspects of neuropathic pain such as touch evoked allodynia and punctate hyperalgesia. By using a combination of methods, the different aspects of nociceptive processing may be teased out and provide mechanistic information to aid decision making. Human experimental pain models can be supportive in understanding the pain mechanisms by exploring the pain system under controlled settings [Standardized stimuli of different modalities (i.e., mechanical, thermal, electrical, or chemical) can be applied to the skin, muscles, and viscera for a differentiated and comprehensive assessment of various pain pathways and mechanisms], the challenge is to match specific treatments to different pain-generating mechanisms.

A detailed description of the chemistry, pharmacology, efficacy, and safety of GSK3838279 is provided in the Investigator's Brochure (IB) [GlaxoSmithKline Document Number [RPS-CLIN-004032](#)]

In light of the global COVID-19 pandemic, all participants will be screened for COVID-19 at the beginning of the study period and will be required to have a negative SARS-CoV-2 test prior to commencing each study period. Please see further details for risk assessment and mitigation strategy below.

2.3. Benefit/Risk Assessment

More detailed information about the known and expected benefits and risks and reasonably expected adverse events of GSK3858279 may be found in the Investigator's Brochure (IB) GlaxoSmithKline Document Number [RPS-CLIN-004032](#)

The risk assessment of GSK3858279 is based on the pre-clinical studies conducted to date and the ongoing First in Human (FiH) study 207804 – GlaxoSmithKline Document Number [2020N429762_00](#).

Summaries of findings from these pre-clinical studies and the FiH study can be found in the IB [GlaxoSmithKline Document Number [RPS-CLIN-004032](#)]

Details of these risks, as well as the risks associated with the procedures, and the proposed strategy to mitigate/monitor these risks are detailed in Section [2.3.1](#).

In this study, safety will be monitored closely both by subjective reporting and by objective means, i.e. serial assessments of vital signs, clinical laboratory information and cardiac monitoring. The study will be run in a clinical unit with access to hospital facilities for the treatment of medical emergencies. Participants will remain monitored in the clinic for a minimum of 2 hours after completion of dosing in each study period and will only be discharged from the unit if the investigator deems it safe to do so.

2.3.1. Risk Assessment

Potential Risk of Clinical Significance	Summary of Data/Rationale for Risk	Mitigation Strategy
Investigational Product (IP)		
Hypersensitivity, including injection site and infusion reactions	
The administration of any (human) mAb has the potential to induce local or systemic immunologic reactions, for example acute allergic reactions (type I) and immune complex disease (ICD) associated with the formation of anti-drug antibodies (ADA) (type III).
 
Non-Clinical
 
In a 13-week study administration of GSK3858279 by weekly IV infusion at 100 mg/kg resulted in infusion reactions after dosing on Days 22 and 29 in one female cynomolgus monkey which was successfully managed in subsequent administrations by pre-treating with anti-histamine.
 
In the 26-week study, there were inflammatory vascular changes in multiple organs of three animals (one female at 10 mg/kg/week and one male and one female at 100 mg/kg/week) as well as mesangioproliferative glomerulopathy in the kidney of the males at 10 mg/kg/week or 100 mg/kg/week, which is consistent with ICD following the formation of ADA. Nonspecific injection site reactions caused by the subcutaneous (SC) dosing route were also noted in some monkeys, which was exacerbated by the immune complex deposition in one male. These findings were considered non-adverse.
 
Animals are not predictive for ADA-mediated adverse reactions in humans, including infusion reactions, hypersensitivity reactions or
	
Participant Selection:
 
Participants with a history of sensitivity to the study medication, or a history of any drug or other allergy that, in the opinion of the investigator, contraindicates their participation, will not be permitted to enter the study.
 
Participants with renal disorders will also be excluded.
 
Participant monitoring:
 
In Part A of FiH study (207804), participants remained in the inpatient facility for 48 hours post dosing to allow adequate monitoring by trained site personnel.
 
In Part B of FiH (207804) and in this study (209973), participants will be monitored for a minimum of two hours post dosing.
 
Emergency resuscitation facilities will also be available.
 
Participants will be instructed in the Informed Consent Form (ICF) as to the signs and symptoms of hypersensitivity reactions and be

Potential Risk of Clinical Significance	Summary of Data/Rationale for Risk	Mitigation Strategy
	
anaphylaxis [Kronenberg, 2017]. Given that GSK3858279 binds a soluble ligand (CCL17) and is Fc disabled, GSK3858279 is not expected to mediate effector functions of antibody dependent cell mediated cytotoxicity or complement dependent cytotoxicity.
 
Clinical
 
During Part A of the FiH study (207804) in healthy participants, there was neither a report of any relevant hypersensitivity reactions nor any clinically significant changes in urinalysis.
	instructed to seek immediate clinical care should they develop.
Immunogenicity	
Monoclonal antibodies may induce ADAs, which have the potential to induce adverse reactions (mentioned above) or affect the PK and PD properties of the drug. GSK3858279 is a human antibody, with a lower potential for ADA formation than a chimeric antibody.
 
Nonclinical
 
In the nonclinical studies a significant number of monkeys treated with GSK3858279 had confirmed ADA, but mostly the presence of ADA did not affect the systemic exposure or PK parameters for GSK3858279, however, there was no impact on clinical observations apart from the animal which had findings consistent with an infusion-related reaction and on the chronic toxicology study, vascular changes consistent with immune complex disease were seen (mentioned above). In general, the incidence and titre of ADA in nonclinical studies are not predictive of the generation of ADAs in humans.
	
Samples will be drawn at baseline and at regular intervals to test for immunogenicity, and participants will be monitored for any evidence of adverse reaction as detailed in the hypersensitivity section of this table.
 
Clinical laboratory safety assessments are included in the study. Urine microscopy and laboratory quantification of proteinuria will be investigated following unexplained dipstick proteinuria or haematuria.

Potential Risk of Clinical Significance	Summary of Data/Rationale for Risk	Mitigation Strategy
	
Clinical
 
In Part A of the FiH study (207804) in healthy participants there was a low incidence of pre-existing ADA and for which titres were low. There was no pattern of increasing incidence or increasing titres of ADAs following escalation of the dose level of GSK3858279 (or placebo) and there was no apparent difference between 3 mg/kg IV vs. 3 mg/kg SC.
	

Risk of Infection
	
The intended pharmacologic effect of GSK3858279 may result in an increase in the frequency and/or severity of infection, as a result of potential changes in immune cell trafficking.
 
Non-Clinical
 
No specific studies have been conducted in nonclinical species to investigate the effect of GSK3858279 on response to viral or bacterial infection.
 
CCL17 has an important role in early responses against skin invading pathogens e.g. CCL17 controls filarial larval entry by limiting mast cell-dependent vascular permeability. Mice deficient for CCL17 had an up to 4-fold higher worm burden compared to controls by day 10 of infection with murine filaria Litomosoides sigmodontis (Specht, 2011). The role of CCL17 in systemic anti-pathogen responses is unclear.
 
In pre-clinical studies, administration of the anti-CCL17 antibody (GSK3858279) for 13 weeks to monkeys did not result in modulation of the immune system as assessed by T-cell dependent antibody response, an assessment of humoral immunity, or of peripheral blood lymphocyte populations as assessed by flow cytometry (see IB for further details). In addition, we are not aware
	
Participant Selection
 
Participants with active or chronic infections or a history of recent or recurrent infections will not be included in the study – see Section 5.2.
 
Participant Monitoring
 
Participants will be monitored for infection. Participants will be instructed in the ICF as to the signs and symptoms of infection, and to contact the site personnel should they develop.

Potential Risk of Clinical Significance	Summary of Data/Rationale for Risk	Mitigation Strategy
	
of any pre-clinical in vitro or in vivo data to suggest a potent immunosuppressive effect of CCL17 blockade. There is, however, no data available to our knowledge of the consequences of CCL17 inhibition/ablation in pre-clinical viral infection models.
 
Clinical During Part A of the FiH study (207804) in healthy participants, there were no reports of infection-related serious adverse events.
	
Vaccination Reactions	
There is a theoretical risk that GSK3858279 could decrease an individual's immune response to vaccines administered while on therapy or to allow symptoms to develop following the administration of live vaccines.
 
Non-Clinical Monkeys dosed with GSK3858279 for 13 weeks did not demonstrate modulation of the immune system as assessed by T-cell Dependent Antibody Response (TDAR), an assessment of humoral immunity, or of peripheral blood lymphocyte populations as assessed by flow cytometry.
	
Participant selection and non-permitted medications: Attenuated live vaccines should not be administered to participants from 1 month prior to dosing of study medication and for five half-lives after dosing of study medication. If indicated, non-live vaccines (e.g. inactivated influenza vaccines) may be administered whilst receiving GSK3858279 based on an assessment of the benefit:risk (e.g. risk of decreased responsiveness).

Cardiac Risks	
Non-Clinical In the 4-week study, review of the heart data (ECG, blood pressure, heart rate, organ weights and histopathology), in monkeys at doses up to 100 mg/kg/week IV and 30 mg/kg/week SC to n=2/sex/group, did not identify any changes compared to controls. In the 13-week study, higher heart weights were noted compared to controls, without any histopathological or functional (ECG, blood
	
Participant Exclusion: Participants with a history of cardiac disease or cardiac abnormalities (including abnormal Troponin T and NT-proBNP) that, in the opinion of the investigator, would compromise cardiac safety will be excluded from the study.

Potential Risk of Clinical Significance	Summary of Data/Rationale for Risk	Mitigation Strategy
	
pressure, heart rate) correlate. The heavier heart weights were not dose-related and generally did not show a consistent pattern of increased absolute weights, relative to body weight or brain weight. Refer to IB [GlaxoSmithKline Document Number RPS-CLIN-004032]
 
] for further details.
 
In the 26-week study, a thorough evaluation to investigate the potential for cardiotoxicity which included ECG, echocardiogram, telemetry (blood pressure, heart rate), serum cardiac troponin I, NT-proBNP, heart weight and histopathology, did not identify any treatment-related effects on the heart following doses up to 100 mg/kg/week SC.
 
GSK3858279 did not bind to human heart in the tissue cross-reactivity studies and there is no known pharmacological mechanism following administration of an anti-CCL17 which would lead to an increase in heart weight. Therefore, the potential effect on heart weights noted in the 13-week study in monkey was not reproducible following 26 weeks of chronic dosing in monkey and is not considered to be clinically significant.
 
Clinical
 
During Part A of the FiH study (207804) in healthy participants, none of the abnormal findings in the ECG parameters were judged to be clinically significant.
	
Participant monitoring: Investigations during screening include ECG, echocardiogram and troponin T and NT-proBNP. TroponinT and NT-proBNP will be monitored after dosing.

Bleeding Risk	CCR4, the receptor for CCL17 is expressed on platelets and both CCL17 and CCL22 activate platelets in vitro. A potential risk of impaired platelet activation and blood clotting exists with CCL17	Participant exclusion and non-permitted medication

Potential Risk of Clinical Significance	Summary of Data/Rationale for Risk	Mitigation Strategy
	
antagonism although at this stage this is theoretical; there are two conflicting reports describing the ability of anti-CCR4 antibodies, to either block CCL17/CCL22 -mediated platelet aggregation ex vivo [Gear, 2001] or to not block platelet function in vitro/ex vivo assays [Hagemann, 2014]. Clinical data with direct inhibitors of CCR4, such as mogamulizumab (approved in Japan for treatment of T cell lymphoma), are not associated with increased bleeding risk.
 
Non-Clinical Although platelet function has not been specifically assessed non-clinically; no effects on platelet counts or clotting times were observed in the monkey studies. Neither were there any reports of excessive bruising nor difficulties in clotting after blood sampling.
 
Clinical There were no reports of any clinically significant bleeding events during Part A of the FiH study (207804) in healthy participants.
	
Participants with a previous or current history of bleeding diathesis will be excluded. Use of anti-coagulants or anti-platelet agents will be prohibited.

Skin Reactions	
Cutaneous adverse clinical effects have been observed in patients with T-cell lymphomas treated with mogamulizumab (anti-CCR4 antibody) including Stevens-Johnson syndrome. This may reflect depletion of immune regulating cells called “Regulatory T cells” within the skin compartment predisposing to cutaneous inflammatory or autoimmune responses. Given that GSK3858279 will only block CCL17, the alternative ligand, CCL22, should offer redundancy to maintain T cell migration. Relevant to this, CCL22 is highly expressed in skin blister fluid [Bouma, 2017].
	
Participant Exclusion Participants with a history of drug-induced skin reactions and Stevens-Johnson Syndrome will be excluded.
 
Participant Monitoring Clinically significant skin reactions will be reviewed by a dermatologist and, if appropriate, a skin biopsy will be requested for histological analysis.

Potential Risk of Clinical Significance	Summary of Data/Rationale for Risk	Mitigation Strategy
	
Clinical
 
There were no reports of any clinically significant skin reactions during Part A of the FiH study (207804) in healthy participants.
	
Study Procedures		
Events related to UVB irradiation	
UV irradiation from sunlight is associated with an increased incidence of skin cancer. UV irradiation is made up of a spectrum of wavelengths with UVB being one of the risk factors for skin cancer. The range of wavelength of UVB used in this study (narrow band range 310-315 nm) is that used for phototherapy to treat skin conditions such as psoriasis. Literature review [Lee, 2005] indicate there was no increased risk of skin cancer in four studies specifically assessing the potential carcinogenic risk of narrow-band UVB, however there is insufficient literature on the number of exposures and risk of long term development of skin cancer at the UVB wavelength to be administered in this study [Hearn, 2008].
	
Participant exclusion Participants with pre-existing risk factor for skin cancer will be excluded (applicable for UVB-MITT population only).
 
Dose of UVB irradiation will be at 2 x MED.

Events related to UVB test	
The UVB test may induce a post-inflammatory hyperpigmentation (PIH) in some cases [Siebenga, 2019]. Typically, at centres performing the UVB inflammatory test, 3xMED (Minimum Erythema Dose) of UVB irradiation is applied to induce sensitisation, however, long-lasting PIH has been associated with 3xMED.
	
Participant exclusion Participants with Fitzpatrick skin type IV, V or VI will be excluded (applicable for UVB-MITT population only).
 
Dose of UV irradiation will be at 2 x MED.
 
Participant Monitoring At the follow-up visit, participants will be assessed to monitor the possible occurrence of the hyperpigmentation.
 
Participants will be informed in the ICF as to the risk of forming PIH at the UV irradiation sites.

Potential Risk of Clinical Significance	Summary of Data/Rationale for Risk	Mitigation Strategy
Other		
SARS-CoV-2	
The current SARS-CoV-2 pandemic can pose a challenge to integrity of the trials, protection of participants' rights, safety and wellbeing and the safety of clinical trial staff. Therefore, risk mitigation strategies will be put in place for this trial and will be evaluated on an ongoing basis for the duration of this trial, or until there is a consensus that the period of the SARS-CoV-2 outbreak in the Netherlands has passed. If the dynamics of the SARS-CoV-2 outbreak change in such a way that the safety of the trial participants and clinical trial staff or integrity of the data collected during this clinical trial cannot be guaranteed the trial will be halted.
 
GSK3858279 on COVID-19 disease
 
CCL17 (and CCL22) are ligands for the CCR4 receptor. The CCR4 receptor is predominantly expressed on Th2 cells, but is also present on some Th1 cells (Kara, 2014). CCL17 is thus likely to mainly be involved in extracellular infections (e.g. parasitic, extracellular bacteria and fungi), rather than intracellular infections (e.g. viral such as COVID-19) although we cannot rule out a role for CCL17 in viral infection.
 
Based on the available information in the Investigators Brochure and outlined in the 'risk on infection' section in this table, above, there is currently no reason to believe that GSK3858279 could 1) increase the susceptibility of trial participants to the SARS-CoV-2 virus, or 2) worsen or mask any COVID-19 signs, symptoms or complications.
	
Participant selection and monitoring
 
Healthy subjects in the current study fall in a low risk category for complications of COVID-19, the disease caused by the SARS-CoV-2 virus. To reduce the risk of SARS-CoV-2 infections among trial participants, measures and procedures based on the advice issued by GSK Global COVID Guidance, the Dutch Centre for Infectious Disease Control (RIVM) and COVID-19 measures declared by the Dutch government will be adhered to as outlined in CHDR SOP GGECOVID. These would include but are not limited to counselling participants regarding the importance of infection control measures such as hand washing, reducing inter-personal contacts as much as possible and participant awareness of potential COVID-19 symptoms.
 
Site trial staff in direct contact and/or within 1.5 m distance of study subjects will receive additional protection via the use of Personal Protective Equipment (PPE) and disinfectants. Guidance for how participants should conduct themselves throughout the study in relation to COVID-19 restrictions are outlined in CHDR SOP GGECOVID


Potential Risk of Clinical Significance	Summary of Data/Rationale for Risk	Mitigation Strategy
		
All trial subjects will be screened for SARS-CoV-2 with a PCR or rapid antigen test:
 
 1) at screening visit Part 1 2) prior to each admission at the clinical unit with at least one overnight stay (i.e. at Day-2/Day-1); and 3) in case of symptoms possibly related to COVID-19. 4) at the final follow up visit. 5) at times as specified in current COVID-19 guidance of CHDR 
Healthy subjects may be excluded from the study if they test positive for SARS-CoV-2 from screening to the end of study treatments. In case of a positive SARS-CoV-2 antigen test result after first dose was administered, a SARS-CoV-2 PCR will be performed for confirmation. In case of discordant results, the PCR result is leading
 
Participants >50 years will be excluded from the study.
 
Protection of Trial Integrity Adherence to the protocol and CHDR SOP GGECOVID protects the integrity of the data

Potential Risk of Clinical Significance	Summary of Data/Rationale for Risk	Mitigation Strategy
		
collected during this clinical trial, as well as participants' data protection rights.
 
COVID-19 Contingency Plan Any subject that presents with COVID-19-related symptoms and/or has a positive SARS-CoV-2 PCR or rapid antigen test will be excluded from (further) participation in the trial and will receive follow-up medical attention per CHDR SOP GGECOVID

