5.2. Exclusion Criteria

Participants are excluded from the study if any of the following criteria apply:

Medical Conditions

1. History or presence of/significant history of or current cardiovascular, respiratory, hepatic, renal, gastrointestinal, endocrine, haematological, or neurological disorders capable of significantly altering the absorption, metabolism, or elimination of drugs; constituting a risk when taking the study intervention or interfering with the interpretation of data
2. Personal or family history of cardiomyopathy.
3. Abnormal blood pressure as determined by the investigator.
4. Symptomatic herpes zoster within 3 months prior to screening.
5. Evidence of active or latent tuberculosis (TB) as documented by medical history and examination, and TB testing: a positive (not indeterminate) QuantiFERON-TB Gold test.

NOTE: The QuantiFERON-TB Gold test can only be used in countries where it is licensed, and the use of this test is dependent on previous treatment(s). This test may not be suitable if previous treatment(s) produced significant immunosuppression.

6. Significant allergies to humanized monoclonal antibodies.
7. Clinically significant multiple or severe drug allergies, intolerance to topical corticosteroids, or severe post-treatment hypersensitivity reactions (including, but not limited to, erythema multiforme major, linear immunoglobulin A (IgA) dermatosis, toxic epidermal necrolysis, and exfoliative dermatitis)
8. Lymphoma, leukaemia, or any malignancy. Those who are at risk of DNA repair diseases or any family history of DNA repair disease.
9. Alanine transaminase (ALT) $>1.5 \times$ upper limit of normal (ULN).
10. Bilirubin $>1.5 \times$ ULN (isolated bilirubin $>1.5 \times$ ULN is acceptable if bilirubin is fractionated and direct bilirubin $<35\%$).
11. Current or chronic history of liver disease or known hepatic or biliary abnormalities (with the exception of Gilbert's syndrome or asymptomatic gallstones).
12. QTc >450 msec

NOTES:

- The QTc is the QT interval corrected for heart rate according to Bazett's formula (QTcB), Fridericia's formula (QTcF), and/or another method, machine-read or manually over-read.
- The specific formula that will be used to determine eligibility and discontinuation for an individual subject will be QTcF. In other words, several different formulae cannot be used to calculate the QTc for an individual subject and then the lowest QTc value used to include or discontinue the subject from the trial.

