- For purposes of data analysis, QTcB, QTcF, another QT correction formula, or a composite of available values of QTc will be used as specified in the Reporting and Analysis Plan (RAP).

13. History of Stevens-Johnson Syndrome.

14. Known immunodeficiency.

15. Participants with an acute, re-current or chronic infection (e.g., osteomyelitis), who have been receiving treatment within three months prior to dosing or individuals with an active infection.

16. Previous or current history of excessive bleeding or coagulation disorders.

17. Previous history of hypertrophic or keloid scarring.

18. Any current, clinically significant, known medical condition in particular any existing conditions that would affect sensitivity to cold (such as atherosclerosis, Raynaud's disease, urticaria, hypothyroidism) or pain (such as disease that causes pain, hypesthesia, hyperalgesia, allodynia, paraesthesia, neuropathy).

19. Participants indicating pain tests intolerable at screening Participants achieving tolerance at >80% of maximum input intensity for cold pressor and electrical pain tests are to be excluded. If pressure pain test tolerance is >80% of maximum input intensity they may be enrolled as per PI judgement

20. History or presence of post-inflammatory hyperpigmentation. Applicable for the participants in the UVB-MITT population only.

21. Participants with Fitzpatrick skin type IV, V or VI. Applicable for the participants in the UVB-MITT population only.

22. Any of the following on the proposed test area on the back: widespread acne, freckles, tattoos, birthmarks or scarring (investigator discretion may be used to determine if small areas may be avoided in the testing area on the back). Applicable for the participants in the UVB-MITT population only.

23. A minimal erythema dose (MED) higher than 355 mJ/cm² at screening. Applicable for the participants in the UVB-MITT population only.

Prior/Concomitant Therapy

24. Past or intended use of over-the-counter or prescription medication including herbal medications within 7 days prior to dosing until after follow-up visit.

25. Live vaccine(s) within 1 month prior to dosing or plans to receive such vaccines during the study.
26. Treatment with biologic agents (such as monoclonal antibodies including marketed drugs) or immunosuppressants within 3 months or 5 half-lives (whichever is longer) prior to dosing.
27. Treatment with anti-platelet or anti-coagulant agents within 7 days of dosing.

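### The risk table says UVB participants with a skin-cancer risk factor are excluded, but no criterion in Section 5.2 carries that exclusion

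*Protocol*

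**What the plan says.** The Protocol's risk table (Section 2.3.1) pairs each risk with mitigation measures, several of which are exclusions. Three matter here.

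- UVB irradiation row: "Participants with pre-existing risk factor for skin cancer will be excluded (applicable for UVB-MITT population only".
- Skin reactions row: "Participants with a history of drug-induced skin reactions and Stevens-Johnson Syndrome will be excluded".
- Infection row: "Participants with active or chronic infections or a history of recent or recurrent infections will not be included in the study", followed by a pointer to Section 5.2.

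Section 2.3.3 then concludes that the risks are minimal and justified, taking account of the measures adopted to reduce them.

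The eligibility rules are in Section 5. Appendix 2 (Section 10.2) names Section 5 as the place where inclusion and exclusion requirements are set out. The opening of Section 5 forbids waivers, and Section 8 requires eligibility to be confirmed against all criteria. The nearest criteria in Section 5.2 are:

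- Criterion 8, for everyone: "Lymphoma, leukaemia, or any malignancy. Those who are at risk of DNA repair diseases or any family history of DNA repair disease".
- Criterion 20, UVB group only: "History or presence of post-inflammatory hyperpigmentation".
- Criterion 21, UVB group only: "Participants with Fitzpatrick skin type IV, V or VI".
- Criteria 22 and 23, UVB group only: local findings on the proposed test area, and a minimal erythema dose (MED) above 355 mJ/cm².
- Criterion 13: "History of Stevens-Johnson Syndrome". Criterion 7 covers multiple or severe drug allergies and severe hypersensitivity reactions. Criterion 47 covers other drug allergy where the investigator or medical monitor judges that it rules out participation.
- Criterion 15: acute, recurrent or chronic infection in participants "who have been receiving treatment within three months prior to dosing or individuals with an active infection".

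**The concern.** A benefit-risk statement should rest on safeguards that the operative criteria apply. If the risk table claims an exclusion that the screening criteria omit, the ethics committee and the participant are told of a protection that depends on someone reading the risk table as an eligibility rule.

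The skin-cancer row matters most. The irradiation is not therapeutic, Section 2.3.2 states that participants gain no direct benefit, and the UVB row itself concedes that the literature on number of exposures and long-term skin-cancer risk at this wavelength is insufficient. In that setting a stated exclusion is a substantive part of the justification.

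**Working it through.** There is no figure to reproduce. The check compares the three risk-table exclusions with all 47 criteria in Section 5.2. The criteria are numbered 1 to 47 without a gap, so none appears to have been lost in the public version.

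**Skin-cancer risk factors.** The risk table excludes any pre-existing risk factor, for the UVB group only. Criterion 8 has a different scope (everyone) and a narrower content (malignancy and DNA repair disease). Of the UVB-only criteria, 20 concerns hyperpigmentation. Criterion 21 is tied by the risk table to hyperpigmentation, in a separate row from cancer risk. Criterion 22 is limited to the skin of the test area, and 23 is an upper limit on MED. No criterion names skin-cancer risk. As an illustration, a UVB candidate with a family history of skin cancer, if the sponsor counts that as a risk factor, meets no explicit exclusion.

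**Drug-induced skin reactions.** The risk table sets no severity limit. Criterion 13 carries over Stevens-Johnson Syndrome in full. Criterion 7 requires multiple or severe allergy or a severe reaction. Criterion 47 is a matter of opinion. What remains uncovered is a past non-severe drug rash that the investigator or medical monitor does not consider a reason to exclude.

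**Infection.** The risk table names active, chronic, recent or recurrent infection with no condition about treatment. Criterion 15 carries active infection in full and the rest only if treated within three months before dosing. On wording alone, recurrent infection last treated four months before dosing, or a recent untreated infection that has resolved, is inside the row and outside the criterion. Criteria 4, 5 and 42 add only named infections (herpes zoster, tuberculosis, SARS-CoV-2). The row, however, refers the reader to Section 5.2, so criterion 15 can be read as its working definition.

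**Is this the protocol's normal pattern?** No. Other exclusions in the risk table do have a counterpart in Section 5: bleeding history (criterion 16), Fitzpatrick type (21), troponin T and NT-proBNP (37), and age above 50 (Section 5.1).

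**Exposure behind the main gap.** The schedule gives UVB application on Day -1 and Day 7 of each period: 2 per period × 3 periods = 6 irradiations per UVB participant at 2 × MED, each on 30 × 30 mm of the back. There are also 6 ascending test doses on 1 × 1 cm areas at screening. About 18 participants are planned for this group.

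**The case against.** Several counter-arguments have force.

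- A reader might infer that sites do enrol such people and that the approved mitigations are not delivered. The documents do not support that. The overtly-healthy requirement in Section 5.1 and criteria 1, 18 and 47 allow an investigator to exclude by judgement, though they do not oblige it. Section 2.3.1 is also protocol text that says these people will be excluded. Much of the stated protection is carried over: malignancy, DNA repair risk, Stevens-Johnson Syndrome, severe reactions, and active or recently treated infection. The supportable statement is that a site could enrol them.
- A reader might also infer that the infection row contradicts criterion 15. It does not clearly do so. The row cites Section 5.2, and Section 2.3.1 leaves recent and recurrent undefined.
- The skin-reactions row was prompted by severe cutaneous effects of an anti-CCR4 antibody, so it may have been meant to cover severe reactions only. That is plausible, but the wording does not say so. The hypersensitivity row does carry an investigator-opinion qualifier, which the skin row lacks.
- Risk factor for skin cancer is never defined. The same row calls UVB itself one of the risk factors, so a literal reading would exclude almost anyone with sun exposure. This stands as a reason why the sponsor must define the term. It does not supply the missing criterion.
- The SAP version history reports that the study was terminated for not meeting the futility threshold. The futility interim was timed after the last UVB participant's Period 3 Day 15 assessments, so a screening change would probably protect no further UVB participant in this trial. The benefit-risk statement would still be inaccurate.

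**Conclusion.** The inconsistency is real and is clearest for skin-cancer risk: Section 2.3.1 states an exclusion that no criterion in Section 5.2 carries, and the conclusion in Section 2.3.3 relies on the stated measures. The drug-induced skin reaction gap is smaller, limited to non-severe reactions not caught by judgement. The infection row is a matter of wording only.

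Its size in people is unknown. It bears on about 18 planned UVB participants for the skin-cancer exclusion and on up to 30 for the skin-reaction exclusion, but the documents do not show how many would have such a history. The conclusion assumes that screening follows Section 5.2, as Appendix 2 indicates.

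A reader might take the finding to mean that the broader wording is the right one and that Section 5.2 must be widened. The documents do not show which scope the sponsor intended, and this review does not judge it. Sample size, error rates, endpoints and the primary analysis are untouched.

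**What to change.** Reconcile Sections 2.3.1 and 5.2 so that both state the same exclusions. Either route works, and the sponsor decides which clinical scope is meant:

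- carry the skin-cancer-risk exclusion into Section 5.2 for the UVB group, with the sponsor defining which factors count, and carry over the drug-induced skin reaction exclusion as well; or
- restate the mitigation column of Section 2.3.1, and the conclusion in Section 2.3.3, so that they claim only what Section 5.2 applies.

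Under either route, align the wording of the infection row with criterion 15.

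The cost is amendment text. If Section 5.2 is widened, add some screening questions and an unknown number of extra screen failures, which depends on how the sponsor defines the risk factors. If no further amendment is made because the trial has ended, the same correction belongs in the benefit-risk text of any later protocol that reuses this table.
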